4. ANALYSIS METHODS

4.1 General principles

The age group classification for adult and adolescent from the predecessor studies will be used in the BORA subgroup analysis. If the patient's age at the time of enrolment in the previous study was between 12 and 17 years old then he/she was considered as part of the adolescent group even if the patient was 18 years old at the time of entry in to BORA study. If it was between 18 and 75 years old, he/she was considered as part of adult group. Actual age calculated at BORA study entry will be used in descriptive summary of age and listings.

Patients randomised to placebo in the predecessor study will be summarised separately from patients randomised to benralizumab. The presentation of treatment group will combine treatment assigned in both BORA and the predecessor study as follows:

- Benra 30 mg q.4 weeks
 - Predecessor q.4 weeks
 - Predecessor placebo
- Benra 30 mg q.8 weeks

- Predecessor q.8 weeks
- Predecessor placebo

The analysis of the primary and secondary endpoints will include all data captured during the study, unless the patient withdraws consent, and assent, where applicable, regardless of whether study treatment was prematurely discontinued or delayed, and/or irrespective of protocol adherence. Any data collected after a patient is transitioned into the long-term extension study MELTEMI will not be included in the analyses described in this SAP.

Summary data will be presented in tabular format by treatment. Categorical data will be summarised by the number and percentage of patients in each category. Continuous variables for parametric data will be summarised by descriptive statistics including n, mean, standard deviation, median, minimum value and maximum value unless otherwise specified.

All endpoints as describe in previous sections will be summarised descriptively. The study is not a confirmatory study, thus in general no hypothesis testing and/or p-values will be provided. Following are sets of planned groups for the study.

The primary source of data for the clinical study report (CSR) summaries will be based on patients who stayed in the BORA study. The analyses will follow the two phases as described in the protocol amendment. Some selective summaries will be separately presented for the patients who enrolled into MELTEMI study.

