3.3 Patient enrolment and randomization

Each patient should meet all of the inclusion criteria and none of the exclusion criteria for this study. Under no circumstances can there be exceptions to this rule.

The Investigator will:

1. Obtain signed informed consent and/or assent as applicable locally (hereafter referred to collectively as 'consent') from the patient, and/or parent or legal guardian, before any study specific procedures are performed at Visit 1
2. Assign each potential patient a unique enrolment number beginning with 'E#' via interactive web/voice response system (IWRS/ IVRS)
3. Determine patient eligibility
4. Assign eligible patient a unique randomization code via IWRS/IVRS

For all adult patients and non-EU adolescent patients previously assigned to the placebo arm in the predecessor study, randomization in this safety extension study will be stratified by the

predecessor study. For patients from the predecessor studies D3250C00017 and D3250C00018, the randomization will be further stratified by age group (adults/adolescents). In addition, the adult patients will be also stratified by country. Specific information concerning the use of the IWRS/IVRS will be provided in the separate manual.

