4.2.3.3 Adolescents within the European Union

Adolescents previously assigned to an active treatment arm in the predecessor study

Adolescents within the European Union (EU) will continue to receive only the Q8W dosing regimen as per the predecessor study. In order to maintain the blind of the predecessor study, this group will receive the injections every 4 weeks for the first 3 doses (active drug at Visits 1 and 3, placebo administered at Visit 2) followed by every 8 weeks thereafter (to match the regimen of the adolescents who were on placebo in the predecessor study).

Adolescents within the EU will thereafter be receiving open label treatment. These adolescent patients will follow an every 4 weeks Study Visit schedule; however, investigational product (IP) will only be administered at every other visit after the first 3 doses as described above.

Adolescents previously assigned to the placebo arm in the predecessor study

Adolescents within the EU who were randomized to placebo in the predecessor study will be assigned to benralizumab 30 mg every 8 weeks in this safety extension study (every 4 weeks for the first 3 doses followed by every 8 weeks thereafter).

After the first 3 doses, adolescent patients within the EU will be receiving open label treatment with IP administered at their bimonthly visit.

With no placebo arm in this safety extension study, adolescent patients within the EU will thus be receiving open label treatment. These adolescent patients will follow an every 4 weeks Study Visit schedule; however, IP will only be administered at every other visit after the first 3 doses as described above.

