6.5 Methods for assigning treatment groups

All adults globally, and adolescents outside the EU who were randomized to benralizumab in the predecessor study will be assigned to the same dosing regimen in this safety extension study as they received in the predecessor study. Patients who were randomized to the placebo arm in the predecessor study will be randomized at Visit 1 of this safety extension study to 1 of the 2 benralizumab dose regimens (in a ratio of 1:1). Randomization codes will be assigned strictly sequentially as patients become eligible for randomization in accordance with stratification in this study. All adolescents within the EU will be assigned to the 30mg every 8 weeks dose regimen regardless of the treatment assignment in the lead-in study.

Patients who fail to meet the inclusion/exclusion criteria should not, under any circumstances, be enrolled or receive study medication. There can be no exceptions to this rule.

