4.1.1 Adult completion analysis

This analysis will be conducted when all adult patients within BORA have completed the study, and the final adolescent patient has completed the first 56 weeks of treatment within BORA. At this time, all of the study objectives related to adults will be fully addressed. The CSR will be prepared for the adult completion analysis as detailed below.

Data cutoff for this analysis will be the date when all adult patients within BORA have completed the study, and the final adolescent patient has completed the first 56 weeks of treatment within BORA. The analysis summary tables and figures will include adult data up to and including follow-up visit and adolescent data up to Week 56 visit or IPD visit, whichever is earlier, while all listings will include all adult data up to and including follow-up visit and adolescent data up to the date of data cut-off (therefore may include adolescent data beyond Week 56 that is not included in any analyses).

Summaries will be presented for patients enrolled from studies D3250C00017 and D3250C00018, separately for patients from study D3250C00020. Adult patients and adolescents will be separately summarised as well as combined.

For the analysis of adolescent data in the adult completion analysis, only on-treatment evaluations will be included in the summaries. For example, for summaries of AEs, only on-treatment AEs will be summarised for adolescents.

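### Adolescent Q8W columns pool open-label EU patients assigned by region, with fewer injections, with blinded non-EU patients; the Q4W columns contain only the latter

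*SAP*

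**What the plan says.** **Reporting groups.** SAP 4.1 states: "The presentation of treatment group will combine treatment assigned in both BORA and the predecessor study as follows". Four groups follow: Q4W from predecessor Q4W, Q4W from predecessor placebo, Q8W from predecessor Q8W, and Q8W from predecessor placebo. SAP 4.1.1 adds: "Adult patients and adolescents will be separately summarised as well as combined". SAP 4.1.2 gives adolescents their own addendum report.

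**EU adolescents.** Protocol 6.5: "All adolescents within the EU will be assigned to the 30mg every 8 weeks dose regimen regardless of the treatment assignment in the lead-in study". Protocol 4.2.3.3 says that those from an active arm "will continue to receive only the Q8W dosing regimen as per the predecessor study", and that "adolescent patients within the EU will thus be receiving open label treatment". Protocol 1.5 and 4.2.3.3 date the open-label phase from after the first 3 doses. The note to Protocol Figure 1 and the footnotes to Tables 2A and 2B say that these patients get no placebo injection at the interim visits thereafter.

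**Non-EU adolescents.** Under Protocol 4.2.3.2, those from an active arm keep their regimen, and those from placebo are re-randomised to Q4W or Q8W (1:1, Protocol 6.5). On Q8W, dummy injections fill the interim visits to keep the blind. Protocol 3.3 introduces the randomisation with "For all adult patients and non-EU adolescent patients previously assigned to the placebo arm in the predecessor study", so predecessor-active patients are not randomised again.

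**Other groupings.** Protocol 8.5.1 and 8.5.2 leave further group variables and subgroups to the SAP. The SAP adds age group, predecessor study, predecessor baseline eosinophil count, ADA status and MELTEMI enrolment. EU and non-EU adolescents are separated only in the flow charts of SAP 1.2 (Figures 2 and 3).

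**The concern.** The second primary objective is the safety and tolerability of two regimens in adolescents. In a study without tests, the side-by-side columns are the analysis, and a reader will compare them.

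The adolescent Q4W columns are entirely non-EU and blinded at site and patient level. Both adolescent Q8W columns may also contain EU patients who know their regimen and who receive fewer injections. The split by predecessor arm does not help, because EU adolescents enter both Q8W columns.

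The number of injections is the most concrete problem. SAP 4.2.5.1 summarises injection-site and hypersensitivity events separately, and Protocol 6.8 requires at least 2 hours of observation after each administration. Fewer injections mean fewer occasions for an injection-site event and fewer observed post-injection periods. The rates per 100 patient-years in SAP 4.2.5.1 do not correct this: planned follow-up is the same for EU and non-EU adolescents, and only the number of injections differs.

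Exacerbations are less directly exposed. Their definition depends on care delivered (systemic corticosteroids, hospital admission, emergency or urgent care), which can vary with local practice.

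**Working it through.** The plan gives no sample size, event count or adolescent number on this point, so there is no figure to reproduce.

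**1. Planned injections per adolescent through Week 104 (Visit 27)**

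- Non-EU, either regimen: one injection (active or dummy) at each of Visits 1 to 27, so 27.
- EU: Visits 1, 2 and 3, then every other visit (5, 7, ..., 27). That is 3 + 12 = 15.
- Difference: 12 of 27, or 44% fewer.
- Through Week 52 (Visit 14), which bears on the adult completion analysis with its adolescent data to Week 56: 14 for non-EU; for EU, Visits 1, 2, 3, 5, 7, 9, 11 and 13, so 8.

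For predecessor-placebo patients, active drug falls at Visits 1, 2, 3, 5, ..., 27 in EU and non-EU Q8W alike, so 15 active doses in each. The gap is made up of dummy injections, not drug exposure.

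**2. EU share of the Q8W column, predecessor-placebo adolescents only**

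Let f be the EU share of predecessor-placebo adolescents. The documents do not give f, so 10% to 50% is assumed. Non-EU patients split 1:1.

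- EU share of Q8W: s = f / (f + (1 − f)/2) = 2f / (1 + f)
- EU share of Q4W: 0
- Mean planned injections in pooled Q8W: 15s + 27(1 − s) = 27 − 12s, against 27 in Q4W
- Shortfall relative to Q4W: 12s / 27

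| f | s | Mean injections, Q8W | Shortfall against Q4W |
|---|---|---|---|
| 10% | 18% | 24.8 | 8% |
| 20% | 33% | 23.0 | 15% |
| 30% | 46% | 21.5 | 21% |
| 50% | 67% | 19.0 | 30% |

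If every injection, active or dummy, carried the same injection-site risk, the last column would also be the expected shortfall in injection-site events per patient in pooled Q8W, with no regimen effect at all.

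**3. Other adverse events, as illustration only**

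With no regimen effect, the apparent Q8W minus Q4W gap is s times the EU minus non-EU difference. If that difference were 10 percentage points (an assumption), the gap would be 1.8 points at f = 10% and 6.7 points at f = 50%.

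**4. With the split**

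Comparing Q4W with non-EU Q8W puts the EU share at 0% and planned injections at 27 in both columns.

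Steps 2 and 3 do not extend to the predecessor-active columns, because the documents do not give the regimen ratio among carried-over adolescents. The direction is the same there, since EU patients again appear only under Q8W.

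**The case against.** The strongest reply is that no regimen contrast is planned. The objective asks for the safety of each regimen, SAP 1.3 disclaims power for any hypothesis, and SAP 4.1 says that in general no tests or p-values will be given. For describing safety on Q8W, including every adolescent on Q8W is legitimate. This stands, and is why the pooled column should stay. It does not make columns printed side by side comparable.

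The blinding argument is also limited. Every patient receives benralizumab, so only the dosing interval is concealed, and the documents do not show that knowing it changes reporting. Nor do they show any regional difference in reporting or care. The injection count needs neither assumption.

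Small numbers are a fair objection. The SAP amendment history calls the adolescents a small group and gives that as the reason for raising the common-event threshold to 5%. Splitting both Q8W columns makes six adolescent groups out of four.

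A reader might infer more than the documents support:

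- That regimen is wholly confounded with region. It is not: non-EU adolescents appear under both regimens.
- That restricting to non-EU adolescents gives a fully randomised comparison. Only those from predecessor placebo are randomised in BORA; the others carry over an earlier allocation and had to complete the predecessor treatment period.
- That the 18% to 67% range describes all adolescent Q8W patients. The 1:1 ratio covers predecessor-placebo patients only.
- That no table will separate the regions. Table shells are not among the documents; what can be said is that the SAP text specifies no such split.

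**Conclusion.** The point holds as partial confounding in descriptive adolescent summaries. Region of assignment, open-label status and number of injections (15 against 27 through Week 104) differ within the Q8W columns and not within Q4W, and the SAP text neither separates nor flags this. Injection-site events are the clearest case, because the imbalance follows from the schedule alone.

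The size depends on the unreported number of EU adolescents. Under the assumed EU share of 10% to 50% among predecessor-placebo adolescents, mean planned injections in that Q8W column fall to between 24.8 and 19.0. No formal test and no adult-only table is affected; the combined adult and adolescent summaries carry the same mix, diluted by adults. This is a worthwhile, inexpensive improvement to the reporting and does not invalidate the study.

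**What to change.** Add to SAP 4.1, with effect in 4.2.5.1 and 4.2.6.1 and in both the adult completion report and the adolescent addendum:

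- In the adolescent adverse-event tables (including injection-site and hypersensitivity events) and exacerbation tables, show Q8W as EU, non-EU and pooled total within each predecessor-arm group, with the number of patients in each.
- State that any Q4W versus Q8W difference in adolescents is read from non-EU patients within predecessor-arm group, and that only the predecessor-placebo group is randomised in BORA.
- Footnote the pooled Q8W columns: they include EU patients assigned by region, open label after the first 3 doses and without interim placebo injections.

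EU membership follows from country, using the list in the protocol footnote, so no new data are needed and nothing changes in conduct or dosing. The cost is a few extra columns, some with very small cells. To limit this, the exacerbation split could be shown without also dividing by eosinophil count.

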4.1.1 Adult completion analysis

This analysis will be conducted when all adult patients within BORA have completed the study, and the final adolescent patient has completed the first 56 weeks of treatment within BORA. At this time, all of the study objectives related to adults will be fully addressed. The CSR will be prepared for the adult completion analysis as detailed below.

Data cutoff for this analysis will be the date when all adult patients within BORA have completed the study, and the final adolescent patient has completed the first 56 weeks of treatment within BORA. The analysis summary tables and figures will include adult data up to and including follow-up visit and adolescent data up to Week 56 visit or IPD visit, whichever is earlier, while all listings will include all adult data up to and including follow-up visit and adolescent data up to the date of data cut-off (therefore may include adolescent data beyond Week 56 that is not included in any analyses).

Summaries will be presented for patients enrolled from studies D3250C00017 and D3250C00018, separately for patients from study D3250C00020. Adult patients and adolescents will be separately summarised as well as combined.

For the analysis of adolescent data in the adult completion analysis, only on-treatment evaluations will be included in the summaries. For example, for summaries of AEs, only on-treatment AEs will be summarised for adolescents.

4.1.2 Adolescent completion analysis

This analysis will be conducted when the final adolescent patient has completed BORA. The analysis will include all data for adolescents up to follow-up visit and will be reported in an addendum report to the CSR.

The data analyses will be conducted using the SAS® System 9.4 (SAS Institute Inc., Cary, NC) or higher version.

4.2 Analysis methods

4.2.1 Patient disposition

The patients from the predecessor studies that sign the informed consent form will be summarised. The number and percentage of patients throughout the study with respect to completion of treatment, completion of the study and discontinuation from the study will be provided. For adolescent patients, number and percentage of adolescent patients who completed treatment, completed the study and discontinued from the study on or prior to the cut-off date will be presented for the adult completion analysis. Patients who enrolled into MELTEMI will be considered as BORA study completers, but will be identified as a separate category in the disposition summary. In addition, the number and percentage of patients in each analysis set will be presented. These analyses will be summarised for patients with predecessor baseline eosinophil count $\geq 300/\mu\text{L}$ and $< 300/\mu\text{L}$.

4.2.2 Demography data and patient characteristics

Demography data such as age, gender, and race will be summarised by treatment group for the FAS. Age at the time of BORA's enrolment will be present. Age group for adult and adolescent will be based on the age group from predecessor studies.

Various baseline characteristics will also be summarised by treatment group based on the full analysis set. These include data (minimum, but not limited to) such as medical, surgical, cardiovascular and respiratory disease histories, weight, height and BMI, history of allergy, FEV₁ (pre and post bronchodilator) at baseline, asthma duration, age at onset of asthma, the use of maintenance oral corticosteroids (yes/no), asthma medications, the number of exacerbations in the previous 12 months, and the number of exacerbations requiring hospitalisations in the previous 12 months. Overall key baseline characteristics, lung function data and respiratory disease characteristics will be summarised for patients with predecessor baseline eosinophil count $\geq 300/\mu\text{L}$ and $< 300/\mu\text{L}$.

Medical and surgical histories will be summarised by MedDRA SOC and MedDRA PT.

All demographic and baseline characteristics data including medical, surgical, cardiovascular and respiratory disease histories will be also summarised for the patients who rolled over to MELTEMI study.

4.2.3 Concomitant medication

The number and percentage of patients who take concomitant medications, and those who take disallowed concomitant medications during the study, will be presented by treatment group. Concomitant medications will be classified according to the AstraZeneca Drug Dictionary (AZDRUG). The summary tables will present data by generic term within ATC code.

The number and percentage of patients taking maintenance asthma medications, including ICS/LABA fixed dose combinations, at baseline will be summarised and for those patients taking ICS and OCS at the study baseline, the converted dose will be summarised. The number of patients treated with ICS and OCS at baseline will be summarised separately by ATC code and preferred term, with total daily dose (non-converted) at baseline summarised for each preferred term. A similar summary will be prepared to summarise total daily dose of OCS at baseline. For patients from ZONDA, all OCS taken at baseline regardless of reason for therapy will be included to be consistent with the way the data was reported and analysed in ZONDA.

All above summaries also will be summarised for the patients who rolled over to MELTEMI study.

4.2.4 Exposure

Exposure to the investigational product will be summarised by treatment group for the full analysis set. Summary of exposure will be also summarised for the patients who rolled over to MELTEMI study.

4.2.5 Analysis methods for safety variables

All safety variables will be summarised for the full analysis set.

4.2.5.1 Adverse events

Adverse events (AEs) will be summarised separately by the treatment group for the on-study, on-treatment and post-treatment periods, as defined in Section 3.1.1.

An overall summary table will be produced showing the number and percentage of patients with at least 1 AE in any of the following categories; AEs, serious adverse events (SAEs), deaths due to AE, and AEs causing discontinuation of the investigational product (DAEs). This summary will also be repeated by baseline blood eosinophil count ($<300/\mu\text{L}$, $\geq 300/\mu\text{L}$) for the on-study and on-treatment periods. The total number of AEs in the different AE categories in terms of AE counts will also be presented (ie, accounting for multiple occurrences of the same event in a patient).

AEs will be summarised by System Organ Class (SOC) and Preferred Term (PT) assigned to the event by MedDRA. For each PT, the number and percentage of patients reporting at least one occurrence will be presented, ie, for a patient multiple occurrences of an AE will only be counted once.

A summary of the most common (frequency of $\geq 5\%$ in any treatment group) AEs will be presented by PT. AEs (by PT) will be summarised by causality and maximum intensity. If a patient reports multiple occurrences of the same AE, the maximum intensity will be taken as the highest recorded maximum intensity (the order being mild, moderate, and severe). SAEs, DAEs, and deaths will also be summarised in separate tables.

Furthermore, events of interests such as injection site adverse events, hypersensitivity adverse events, adjudicated MACE+, and malignancies will be summarised separately.

The rate of AEs per person-years at risk, calculated as (number of patients reporting AE)/(total period with patients at risk of AE), will be reported for the on-study, post-treatment and on-treatment periods. The total period at risk for each patient within each study period will follow the definitions specified in Sections 3.1.1. Rates will typically be expressed in terms of events per 100 patient-years.

Separate listings of patients with AEs, SAEs, death due to AE, discontinuations due to AEs, as well as events of interest will be presented.

For the patients who rolled over to MELTEMI study, selective AE and SAE tables during study period will be summarised by treatment group. A listing of adjudicated MACE+ and malignancies will be also provided.

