1.2 Rationale for conducting this study

The treatment options for patients who remain uncontrolled by ICS-LABA are extremely limited.

In previous clinical studies, benralizumab administration resulted in rapid and prolonged depletion of eosinophils in the peripheral blood and in the asthmatic airway with associated improvements in multiple metrics of asthma control. The purpose of this study is to continue to characterize the safety profile of benralizumab administration in asthma patients who have completed 1 of the 3 predecessor studies: D3250C00017, D3250C00018, or D3250C00020.

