4.1 Enrolment period

4.1.1 Randomization (Visit 1)

Each potential patient or parent/legal guardian (as applicable) will provide written informed consent prior to any study specific procedures and undergo assessments applicable for the visit (see [Table 1](#) or [Table 2](#)).

In order to provide sufficient time for patients to consider participation in this study, and to ensure an uninterrupted dosing regimen as patients transition between the predecessor study and this study, patients will be provided with the ICF at/after the visit at which they receive their last dose of IP in the predecessor study and will be asked to sign the ICF at Visit 1 of this study, prior to any study-specific procedures being performed.

Visit 1 of this study will be scheduled to ensure an uninterrupted dosing regimen as patients transition between the predecessor study and this safety extension study. Therefore, if the actual EOT visit in the predecessor study occurs more than 7 days from the scheduled EOT visit, the patient will not be eligible to enrol in this study. The End-of-Treatment (EOT) visit for the predecessor study and Visit 1 for this study will occur on the same day and will include the first dose of IP for this study. If IP cannot be administered at this visit, the patient will not be eligible for enrolment in this study.

As Visit 1 coincides with the EOT visit of the predecessor study, repeated assessments (see [Table 1](#) and [Table 2](#)) are not required, as data will be duplicated programmatically between the 2 study databases, as applicable. As electronic patient-reported outcome (PRO) devices were used to capture ACQ6, AQLQ(S)+12, WPAI+CIQ, EQ-5D-5L in the predecessor studies, the patient does not need to complete the paper versions of these at Visit 1 of this safety extension study.

Registration of patient's enrolment via IWRS/IVRS should occur on day when other Visit 1 procedures are done.

Visit 1 assessments are primarily concerned with confirmation of the patient eligibility for the extension study

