5.2.5 Safety laboratory tests

Safety laboratory tests (list provided in [Table 3](#) and [Table 4](#)) will be performed in a central laboratory. For information on methods of collection, assessment, labelling, storage and shipment of samples, please refer to the separate Laboratory Manual. Safety samples will be collected in accordance with the schedules provided in [Table 1](#) or [Table 2](#).

Hematology and urinalysis will be assessed in line with the schedules provided in [Table 1](#) or [Table 2](#). A detailed schedule of the chemistry tests is presented in [Table 3](#) and [Table 4](#). Visit 1 of this study is to be combined with the EOT visit of the predecessor study (see [Section 4.1.1](#)), therefore safety laboratory tests performed at the EOT visit in the predecessor study will be considered as baseline for this safety extension study. NB: As the required list of safety laboratory tests at Visit 1 of this safety extension study differs from those collected at EOT of the predecessor studies, the additional parameters required for this study (ie, those not required at the EOT visit of the predecessor study) will only be reported in this study to avoid duplicate reporting. Refer to the separate Laboratory Manual for more details.

Laboratory results should be reviewed by the Investigator/authorized delegate and evaluated for abnormalities. Any laboratory abnormalities considered significant in the Investigators'/authorized delegate's judgement should be reported as described to in [Section 7.1.3](#).

The copy of the laboratory results report should be signed and date by Investigator and retained at the study center.

Table 3 List of safety laboratory tests

Serum chemistry		Hematology	Urinalysis
Alkaline phosphatase	Gamma-GT (gamma-glutamyl transpeptidase)	Hematocrit	Appearance
ALT (alanine aminotransferase)	Glucose	Hemoglobin	Blood
AST (aspartate aminotransferase)	Phosphorus	Mean corpuscular volume (MCV)	Colour
BUN (blood urea nitrogen)	Potassium	Platelet count	Glucose
Calcium	Sodium	Red blood cell (RBC) count	Ketones
Chloride	Total bilirubin	WBC count with differential ^a	Microscopy including WBC/high power field (HPF), RBC/HPF
CO ₂ (carbon dioxide)	Total cholesterol		pH
Creatinine	Uric acid		Specific gravity
Serum concentration ^b			

^a Eosinophil, basophil and monocyte counts will be redacted from the central laboratory reports

^b For patients who are on theophylline or digoxin (see Section 3.5.2.2)

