2.4 Baseline and change from baseline

In general, the last non-missing value on or prior to the first dose of IP in BORA will be used as the baseline. The last evaluable post-dose record from the predecessor studies will also be

considered in the selection of baseline value for BORA study. If there is no assessment present, then the baseline value will not be imputed and will be set as missing. Exceptions for both pre-bronchodilator (pre-BD) and post-bronchodilator (post-BD) FEV₁ as specified below.

For pre-BD FEV₁, the following hierarchy rules will be applied to derive baseline:

- Step 1: Select values with acceptable quality (acceptable or borderline quality grade) on the same date closest to the first IP dose in BORA. If the assessments are on the same day of the first IP dose, only the assessments on or prior to the IP dose are used.
- Step 2: If there are central and local spirometry assessments on the same day, central spirometry assessments will be used.
- Step 3: If there are multiple assessments with different times, the earliest assessment will be used.
- Step 4: If there are multiple assessments with the same date and time, the value recorded in the BORA study database will be used.

For post-BD FEV₁, the baseline will be derived independently from pre-BD FEV₁ assessments. With exception from Step 2 to select the highest value within central or local spirometry, the same hierarchy rules as explained above will be applied.

Change from baseline will be calculated as the post-baseline assessment value minus the baseline assessment value. If either value is missing, then the change from baseline value will be missing.

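### The adverse-event overview by eosinophil count uses an unqualified baseline, which SAP 2.4 makes the BORA-entry count, normally an on-treatment value for patients from benralizumab arms

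*SAP*

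**What the plan says.** SAP 4.2.5.1 plans an overview of patients with any adverse event, serious adverse events, deaths, and events leading to discontinuation of study drug. It then adds "This summary will also be repeated by baseline blood eosinophil count", with strata below 300/µL and at or above 300/µL, for the on-study and on-treatment periods. The section does not define that baseline.

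SAP 2.4 supplies the default: in general, "the last non-missing value on or prior to the first dose of IP in BORA will be used as the baseline". It goes on: "The last evaluable post-dose record from the predecessor studies will also be" considered when the value is selected. The only exceptions it names are pre- and post-bronchodilator FEV1.

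Protocol 5.2.5 is consistent with this for laboratory data: "safety laboratory tests performed at the EOT visit in the predecessor study will be considered as baseline for this safety extension study". The white-cell differential is among those tests (Table 3). The table's footnote, "Eosinophil, basophil and monocyte counts will be redacted from the central laboratory reports", concerns what the reports show. It does not say the counts go unmeasured, and SAP 4.2.6.3 analyses their change from baseline.

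**The concern.** The 300/µL cut is meant to separate two kinds of patient by eosinophil level. That works only if the count was taken before the drug could change it. BORA patients come from both active and placebo arms, so a count at BORA entry does not have the same meaning for everyone.

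SAP 4.1 puts the two groups in separate columns: "Patients randomised to placebo in the predecessor study will be summarised separately from patients randomised to benralizumab". With a BORA-entry count, the stratum below 300/µL would hold different kinds of patient in neighbouring columns of the same table. It would also differ from the stratum of the same name in the disposition, baseline, efficacy, patient-reported-outcome and resource-use tables. A reader could not then set the adverse-event overview beside efficacy for the same eosinophil subgroup. Protocol 1.4 makes that comparison a natural one: it reports that benefit appeared greatest at 300/µL or more, and it says that information on eosinophil levels and benefit/risk will be collected.

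**Working it through.** No sample-size or power figure is involved. The check compares the wording and then traces the definition.

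**Step 1. Every SAP analysis section that uses the 300/µL cut**

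| SAP section | Baseline named |
|---|---|
| 4.2.1 Disposition | predecessor |
| 4.2.2 Demography and characteristics | predecessor |
| 4.2.5.1 Adverse events | not qualified |
| 4.2.6 Efficacy | predecessor |
| 4.2.7 Patient-reported outcomes | predecessor |
| 4.2.8 Healthcare resource use | predecessor |

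Five of the six specify the predecessor baseline; 4.2.5.1 does not.

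**Step 2. What the unqualified word resolves to.** Under SAP 2.4 it is the last value on or before the first BORA dose. Eosinophils are not excepted, and nothing in 4.2.5 or 4.2.5.1 overrides the rule. The SAP does use the BORA-entry count elsewhere: 4.2.6.3 summarises change from baseline in eosinophils, again without qualification. The plan therefore has two eosinophil baselines, and the word *predecessor* is what tells them apart.

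**Step 3. Is the BORA-entry count on treatment?** Protocol 4.1.1 puts Visit 1 on the day of the predecessor end-of-treatment visit and states: "Visit 1 of this study will be scheduled to ensure an uninterrupted dosing regimen as patients transition between the predecessor study" and BORA. For patients from the Q4W and Q8W arms, the value is therefore normally an on-treatment one. For patients from placebo it precedes any benralizumab.

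**Step 4. Does treatment move the variable?** Protocol 1.2 says that "benralizumab administration resulted in rapid and prolonged depletion of eosinophils in the peripheral blood".

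**Step 5. How much depletion changes the stratum.** A patient from a benralizumab arm with pre-treatment count X ≥ 300/µL falls below the cut when the fractional depletion exceeds 1 − 300/X. The X values below are illustrative and do not come from the documents.

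- X = 400: 1 − 300/400 = 0.25
- X = 600: 1 − 300/600 = 0.50
- X = 1000: 1 − 300/1000 = 0.70
- X = 1500: 1 − 300/1500 = 0.80

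A patient already below 300/µL stays in the lower stratum if the count falls. Depletion therefore moves patients in one direction only, from the upper stratum to the lower, and only in the predecessor-active columns.

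**The case against.** The strongest reply is that this is one omitted word and not a decision. Five sections share the cut and name the predecessor baseline, two of them (disposition and baseline characteristics) in the same part of the SAP. SAP 2.4 opens with a general rule, not an absolute one. A programmer who knew the study would probably use the right variable. That may well be so, and nothing shows that anyone intended a BORA-entry split. Still, the intent has to be inferred against a written default, and a programmer who follows 2.4 as written would build a different table.

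On weight, the objection is largely right. SAP 1.3 says the study is not powered for any hypothesis test. The unsplit adverse-event tables, the events-of-interest tables, the exposure-adjusted rates and the listings do not depend on this variable. Tables by system organ class and preferred term are not planned by eosinophil count, so the comparison with efficacy that would be lost is confined to this overview. The thresholds in step 5 show how a patient changes stratum, not how many would.

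A split on the entry count could also be defended, since Protocol 1.4 raises theoretical risks from prolonged eosinophil depletion. The SAP gives no such rationale, and the same cut would still mean different things in the active and placebo columns.

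Separately, 4.2.5.1 does not exempt ZONDA from the split, whereas 4.2.6 to 4.2.8 do. That text is determinate and agrees with 4.2.1 and 4.2.2, so it is not an error.

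**Conclusion.** The concern holds. As written, the eosinophil split of the adverse-event overview rests on the BORA-entry count. Its strata are then not comparable between the predecessor-active and predecessor-placebo columns, nor with the strata used in the other five sections.

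The reach is limited to one descriptive overview, repeated for two study periods. How many patients would be misplaced is unknown. The direction rests on the protocol's own statement that the drug depletes eosinophils, and on the reading that SAP 2.4 applies wherever the SAP does not say otherwise. If the sponsor already intended the predecessor baseline, the planned analysis is sound and only the text is wrong. It should be corrected, but it does not threaten the study's main safety results.

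**What to change.** In SAP 4.2.5.1, insert *predecessor* before *baseline blood eosinophil count*, so that the overview uses the same variable as 4.2.1, 4.2.2 and 4.2.6 to 4.2.8. If a split on the BORA-entry count is wanted for a safety reason, add it as a separate table, labelled as such and with its rationale.

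A sentence confirming whether the ZONDA overview is to be split at 300/µL would be helpful but is optional.

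The cost is one word. The predecessor baseline count is already required by five sections, so no new data or derivation is needed. Protocol 8.1 allows SAP amendments to be documented ahead of database lock.
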